11.4.5 Second Malignancy

A ***second malignancy*** is one unrelated to the treatment of a prior malignancy (and is NOT a metastasis from the initial malignancy). Second malignancies require ONLY routine reporting via CDUS unless otherwise specified.

11.4.6 Pregnancy, Pregnancy Loss, and Death Neonatal

NOTE: When submitting CTEP-AERS reports for “Pregnancy”, “Pregnancy loss”, or “Neonatal loss”, the Pregnancy Information Form, available at:

http://ctep.cancer.gov/protocolDevelopment/electronic_applications/docs/PregnancyReportForm.pdf, needs to be completed and faxed along with any additional medical information to [contact]. The potential risk of exposure of the fetus to the investigational agent(s) or chemotherapy agent(s) should be documented in the “Description of Event” section of the CTEP-AERS report.

11.4.6.1 Pregnancy

Patients who become pregnant on study risk intrauterine exposure of the fetus to agents that may be teratogenic. For this reason, pregnancy needs

to be reported in an expedited manner via CTEP-AERS as **Grade 3** “*Pregnancy, puerperium and perinatal conditions - Other (pregnancy)*” under the “*Pregnancy, puerperium and perinatal conditions*” SOC.

Pregnancy needs to be followed **until the outcome is known**. If the baby is born with a birth defect or anomaly, then a second CTEP-AERS report is required.

11.4.6.2 **Pregnancy Loss (Fetal Death)**

Pregnancy loss is defined in CTCAE as “*Death in utero*.” Any Pregnancy loss should be reported expeditiously, as **Grade 4** “*Pregnancy loss*” under the “*Pregnancy, puerperium and perinatal conditions*” SOC. Do NOT report a pregnancy loss as a Grade 5 event since CTEP-AERS recognizes any Grade 5 event as a patient death.

11.4.6.3 **Death Neonatal**

Neonatal death, defined in CTCAE as “*Newborn death occurring during the first 28 days after birth*”, should be reported expeditiously as **Grade 4**, “*Death neonatal*” under the “*General disorders and administration*” SOC, when the death is the result of a patient **pregnancy or pregnancy in partners of men on study**. Do NOT report a neonatal death resulting from a patient pregnancy or pregnancy in partners of men on study as a Grade 5 event since CTEP-AERS recognizes any Grade 5 event as a patient death.

11.5 **Reporting Requirements for Specialized AEs**

11.5.1 Baseline AEs

Although a pertinent positive finding identified on baseline assessment is not an AE, when possible it is to be documented as “Course Zero” using CTCAE terminology and grade. An expedited AE report is not required if a patient is entered on a protocol with a pre-existing condition (e.g. elevated laboratory value, diarrhea). The baseline AE must be re-assessed throughout the study and reported if it fulfills expedited AE reporting guidelines.

- a. If the pre-existing condition worsens in severity, the investigator must reassess the event to determine if an expedited report is required.
- b. If the AE resolves and then recurs, the investigator must re-assess the event to determine if an expedited report is required.
- c. No modification in grading is to be made to account for abnormalities existing at baseline.

11.5.2 Persistent AEs

A persistent AE is one that extends continuously, without resolution between treatment cycles/courses.

ROUTINE reporting: The AE must be reported only once unless the grade becomes more severe in a subsequent course. If the grade becomes more severe the AE must be reported again with the new grade.

EXPEDITED reporting: The AE must be reported only once unless the grade becomes more severe in the same or a subsequent course.

11.5.3 Recurrent AEs

A recurrent AE is one that occurs and resolves during a cycle/course of therapy and then reoccurs in a later cycle/course.

ROUTINE reporting: An AE that resolves and then recurs during a subsequent cycle/course must be reported by the routine procedures.

EXPEDITED reporting: An AE that resolves and then recurs during a subsequent cycle/course does not require CTEP-AERS reporting unless:

- 1) The grade increases OR
- 2) Hospitalization is associated with the recurring AE.

11.6 **Exceptions to Expedited Reporting**

An expedited report may not be required for a specific protocol where an AE is listed as expected. The exception or acceptable reporting procedures will be specified in the protocol. The protocol specific guidelines supersede the NCI Adverse Event Reporting Guidelines. These special situations are listed under the CTEP-AERS reporting Table A for this protocol.

11.7 **Reporting Requirements - Investigator Responsibility**

Clinical investigators in the treating institutions and ultimately the Study Chair have the primary responsibility for AE identification, documentation, grading, and assignment of attribution to the investigational agent/intervention. It is the responsibility of the treating physician to supply the medical documentation needed to support the expedited AE reports in a timely manner.

Note: All expedited AEs (reported via CTEP-AERS) must also be reported via routine reporting. Routine reporting is accomplished via the Adverse Event (AE) Case Report Form (CRF) within the study database.

11.8 **General Instructions for Expedited Reporting via CTEP-AERS**

The reporting methods described below are specific for clinical trials evaluating agents for which the IND is held by COG, an investigator, or a pharmaceutical company. It is important to note that these procedures differ slightly from those used for reporting AEs for clinical trials for which CTEP holds the IND.

The descriptions and grading scales found in the revised NCI Common Terminology Criteria for Adverse Events (CTCAE) version 5.0 will be utilized for AE reporting. All appropriate treatment areas should have access to a copy of the CTCAE version 5.0. A copy of the CTCAE version 5.0 can be downloaded from the CTEP web site at:

http://ctep.cancer.gov/protocolDevelopment/electronic_applications/ctc.htm.

An expedited AE report must be submitted electronically via CTEP-AERS at:
<https://eapps-ctep.nci.nih.gov/ctepaers>.

- Expedited AE reporting timelines are defined as:
 - **24-Hour; 5 Calendar Days** - The AE must initially be reported via CTEP-AERS within 24 hours of learning of the event, followed by a complete expedited report within 5 calendar days of the initial 24-hour report.
 - **7 Calendar Days** - A complete expedited report on the AE must be submitted

within 7 calendar days of the investigator learning of the event.

- Any event that results in a persistent or significant incapacity/substantial disruption of the ability to conduct normal life functions, or a congenital anomaly/birth defect, or is an IME, which based upon the medical judgment of the investigator may jeopardize the patient and require intervention to prevent a serious AE, must be reported via CTEP-AERS **if the event occurs following investigational agent administration.**
- Any death occurring within 30 days of the last dose, regardless of attribution to an agent/intervention requires expedited reporting **within 24 hours** via e-mail to the COG CTEP-AERS Coordinator and Study Chair.
- Any death occurring greater than 30 days of the last dose with an attribution of possible, probable, or definite to an agent/intervention requires expedited reporting **within 24 hours** via e-mail to the COG CTEP-AERS Coordinator and Study Chair.

CTEP-AERS Medical Reporting includes the following requirements as part of the report: 1) whether the patient has received at least one dose of an investigational agent on this study; 2) the characteristics of the adverse event including the *grade* (severity), the *relationship to the study therapy* (attribution), and the *prior experience* (expectedness) of the adverse event; 3) the Phase (1, 2, or 3) of the trial; and 4) whether or not hospitalization or prolongation of hospitalization was associated with the event.

Fax or email supporting documentation **for AEs related to investigational agents** to COG: [contact]; email: [contact]; Attention: COG AERS Coordinator.

- **ALWAYS include the ticket number on all faxed documents.**
- **Use the NCI protocol number and the protocol-specific patient ID provided during trial registration on all reports.**

11.9 Reporting Table for Late Phase 2 and Phase 3 Studies – Table A

Expedited Reporting Requirements for Adverse Events that Occur on Studies under an IND/IDE within 30 Days of the Last Administration of the Investigational Agent/Intervention¹

FDA REPORTING REQUIREMENTS FOR SERIOUS ADVERSE EVENTS (21 CFR Part 312)				
NOTE: Investigators MUST immediately report to the sponsor (COG) ANY Serious Adverse Events, whether or not they are considered related to the investigational agent(s)/intervention (21 CFR 312.64). An adverse event is considered serious if it results in ANY of the following outcomes:				
1) Death. 2) A life-threatening adverse event. 3) Any AE that results in inpatient hospitalization or prolongation of existing hospitalization for ≥ 24 hours. This does not include hospitalizations that are part of routine medical practice. 4) A persistent or significant incapacity or substantial disruption of the ability to conduct normal life functions. 5) A congenital anomaly/birth defect. 6) Important Medical Events (IME) that may not result in death, be life threatening, or require hospitalization may be considered serious when, based upon medical judgment, they may jeopardize the patient or subject and may require medical or surgical intervention to prevent one of the outcomes listed in this definition. (FDA, 21 CFR 312.32; ICH E2A and ICH E6.)				

ALL SERIOUS adverse events that meet the above criteria **MUST** be immediately reported to the NCI via CTEP-AERS within the timeframes detailed in the table below.

Hospitalization	Grade 1 Timeframes	Grade 2 Timeframes	Grade 3 Timeframes	Grade 4 & 5 Timeframes
Resulting in Hospitalization ≥ 24 hrs		7 Calendar Days		24-Hour Notification 5 Calendar Days
Not resulting in Hospitalization ≥ 24 hrs	Not Required		7 Calendar Days	

NOTE: Protocol specific exceptions to expedited reporting of serious adverse events are found in the Specific Protocol Exceptions to Expedited Reporting (SPEER) portion of the CAEPR. Additional Special Situations as Exceptions to Expedited Reporting are listed below.

Expedited AE reporting timelines are defined as:

“24-Hour; 5 Calendar Days” - The AE must initially be reported via CTEP-AERS within 24 hours of learning of the AE, followed by a complete expedited report within 5 calendar days of the initial 24-hour notification.

“7 Calendar Days” - A complete expedited report on the AE must be submitted within 7 calendar days of learning of the AE.

¹SAEs that occur more than 30 days after the last administration of investigational agent/intervention and have an attribution of possible, probable, or definite require reporting as follows:

Expedited 24-hour notification followed by complete report within 5 calendar days for:

- All Grade 4, and Grade 5 AEs

Expedited 7 calendar day reports for:

- Grade 2 adverse events resulting in hospitalization or prolongation of hospitalization
- Grade 3 adverse events

11.10 Protocol Specific Additional Instructions and Reporting Exceptions**For Regimen A and Regimen B:**

- **Grade 1-2 dehydration or Grade 3 dehydration \leq 3 days duration does not require expedited reporting**
- **Grade 1-3 irritability does not require expedited reporting**
- **Grade 1-3 urine output decreased does not require expedited reporting**
- **Grade 1-2 decrease in vision or Grade 3 decrease in vision that resolves within 7 days of onset does not require expedited reporting**
- **Grade 1-3 capillary leak does not require expedited reporting**
- **Grade 1-3 anemia does not require expedited reporting**
- **Grade 1-3 white blood cell or neutrophil count decrease do not require expedited reporting**

11.11 Reporting of Adverse Events for commercial agents – CTEP-AERS abbreviated pathway

The following are expedited reporting requirements for adverse events experienced by patients on study who have not received any doses of an investigational agent on this study. Commercial reporting requirements are provided in Table B.

COG requires the CTEP-AERS report to be submitted **within 7 calendar days** of learning of the event.

Table B

Reporting requirements for adverse events experienced by patients on study who have NOT received any doses of an investigational agent on this study.

CTEP-AERS Reporting Requirements for Adverse Events That Occur During Therapy with a Commercial Agent or Within 30 Days¹

Attribution	Grade 4		Grade 5
	Unexpected	Expected	
Unrelated or Unlikely			CTEP-AERS
Possible, Probable, Definite	CTEP-AERS		CTEP-AERS

¹This includes all deaths within 30 days of the last dose of treatment with a commercial agent, regardless of attribution. Any death that occurs more than 30 days after the last dose of treatment with a commercial agent that can be attributed (possibly, probably, or definitely) to the agent and is not due to cancer recurrence must be reported via CTEP-AERS.

11.12 Routine Adverse Event Reporting

Note: The guidelines below are for routine reporting of study specific adverse events on the COG case report forms and do not affect the requirements for CTEP-AERS reporting.

Routine reporting is accomplished via the Adverse Event (AE) Case Report Form (CRF) within the study database. For this study, routine reporting will include all toxicities reported via CTEP-AERS and all Grade 3 and higher Adverse Events.

12.0 STUDY REPORTING AND MONITORING

The Case Report Forms and the submission schedule are posted on the COG web site with each protocol under “*Data Collection/Specimens*”. A submission schedule is included.

12.1 CDUS

This study will be monitored by the Clinical Data Update System (CDUS) Version 3.0. Cumulative protocol- and patient-specific CDUS data will be submitted quarterly to CTEP by electronic means. Reports are due January 31, April 30, July 31 and October 31. CDUS reporting is not a responsibility of institutions participating in this trial.

12.2 Data and Safety Monitoring Committee

To protect the interests of patients and the scientific integrity for all clinical trial research by the Children's Oncology Group, the COG Data and Safety Monitoring Committee (DSMC) reviews reports of interim analyses of study toxicity and outcomes prepared by the study statistician, in conjunction with the study chair's report. The DSMC may recommend the study be modified or terminated based on these analyses.

Toxicity monitoring is also the responsibility of the study committee and any unexpected frequency of serious events on the trial are to be brought to the attention of the DSMC. The study statistician is responsible for the monitoring of the interim results and is expected to request DSMC review of any protocol issues s/he feels require special review. Any COG member may bring specific study concerns to the attention of the DSMC.

The DSMC approves major study modifications proposed by the study committee prior to implementation (e.g. termination, dropping an arm based on toxicity results or other trials reported, increasing target sample size, etc.). The DSMC determines whether and to whom outcome results may be released prior to the release of study results at the time specified in the protocol document.

13.0 PATHOLOGY GUIDELINES AND SPECIMEN REQUIREMENTS

No pathology review is planned for this study.

14.0 SPECIAL STUDIES SPECIMEN REQUIREMENTS

If the patient consents to banking, any specimens left over after the required and optional research studies described below have been performed will be banked at the Biopathology Center for future research studies.

A table of specimens to be collected is available in [Appendix X](#).

14.1 Required Studies

All patients who provide consent will be eligible for all special studies on ANBL1821.

14.1.1 Immune profiling: Immune phenotyping

14.1.1.1 Specimen Schedule and Requirements

At each time point, collect either two sodium heparin (green top) tubes with 5 mL each of peripheral blood or one sodium heparin (green top) 10 mL tube (total of 10 mL).

Samples are requested at the following time points:

- Pre-therapy (between study enrollment and start of therapy)
- Cycle 1, Day 1 (Regimen B only)
- Cycle 1, post-completion of dinutuximab (collect a single sample between Day 6 and Day 9)
- Cycle 2, Day 1 (prior to initiation of Cycle 2 therapy)

Please do not collect the first sample until you contact the Children's Clinical Translation Discovery Core at Emory ([contact]) to coordinate the date of first sample delivery, and before shipping each sample.

14.1.1.2 Specimen Processing

Samples must be shipped the same day as collected. Sites should plan ahead to avoid Friday or Saturday sample collection. Sample should not be refrigerated or frozen. Samples should be kept at room temperature until shipped. Specimen will be shipped at room temperature for overnight delivery.

14.1.1.3 Specimen Labeling

Tubes must be labeled with:

- The patient's COG ID number
- Specimen type (blood)
- Collection time point (e.g. Cycle 1, Day 6)
- Date collected

14.1.1.4 Specimen Shipping

These specimens will be shipped by FedEx Priority Overnight delivery directly to the Emory University Children's Clinical and Translational Discovery Core (CCTDC).

The peripheral blood sample for immune profiling by flow cytometry should be sent on the same day it was obtained. The sample should be shipped at room temperature overnight via FedEx Priority Overnight delivery.

Samples should only be shipped on Mondays-Thursdays to allow for weekday delivery. NO Friday or Saturday shipments will be allowed.

Please do not collect the first sample until you contact the Children's Clinical Translation Discovery Core at Emory ([contact]) to coordinate the date of first sample delivery, and before shipping each sample.

Specimens should be shipped the same day they are collected at room temperature but in an insulated Styrofoam container (provided by the institution) to prevent temperature fluctuations by Federal Express Priority Overnight delivery to the following address:

For questions about sample processing and shipping, please contact the CCTDC directly.

14.1.1.5 Methodology

We will obtain preliminary data regarding the number of T, B, and NK cells present in the circulation at baseline and after treatment with DFMO and the DFMO/chemo-immunotherapy combination. This T-B-NK panel quantifies these cells using flow cytometry. We will also freeze peripheral blood mononuclear cells (PBMCs), RNA and DNA for these immunogenomic studies.

Flow cytometry panel:

Lineage Panel	Live/Dead (L/D), CD45, CD3, CD4, CD8, CD19, CD14, CD45RA, CCR7, CD25, CD127, HLA-DR
NK Cell Panel	L/D, CD45, CD3, CD8, CD16, CD56, CD57, CD107a, CD158, CD314, CD335

14.1.2 Immune profiling: Cytokine analysis

14.1.2.1 Specimen Schedule and Requirements

At each time point, collect 5 mL of peripheral blood in a sodium heparin (green top) tube and process for plasma.

Samples are requested at the following time points:

- Pre-therapy (between study enrollment and start of therapy)
- Cycle 1, Day 1 (Regimen B only)
- Cycle 1, post-completion of dinutuximab (collect a single sample between Day 6 and Day 9)
- Cycle 2, Day 1 (prior to initiation of Cycle 2 therapy)

14.1.2.2 Specimen Processing

Process the sample within 30 minutes of collection. Centrifuge the blood at 1200 x g for 15 minutes at 4°C (preferred) or room temperature to separate the plasma (top layer) from the red blood cells (bottom, red layer). Quickly, evenly dispense (aliquot) the plasma into pre-labeled cryoprotective vials and cap the vials securely. Place a minimum of 0.25 mL into each cryovial. Immediately freeze the vials upright in a -70°C to -80°C freezer. Store frozen until ready for shipment.

14.1.2.3 Specimen Labeling and Shipping

Each cryovial must be labeled with:

- The patient's COG ID number
- Specimen type (plasma)
- Collection time point (e.g. Cycle 1, Day 1)
- Date collected

Plasma for cytokine analysis can be batched and shipped on dry ice to the **Emory University Children's Clinical and Translational Discovery Core (CCTDC)** after the Cycle 2, Day 1 sample is drawn and processed.

Specimens should be shipped on dry ice in an insulated Styrofoam container (provided by the institution) to prevent temperature fluctuations. Ship by Federal Express Priority Overnight delivery (see [Section 14.1.1](#)). See [Section 14.1.1.4](#) for shipping instructions and address.

14.1.2.4 Methodology

The Emory University Children's Clinical and Translational Discovery Core (CCTDC) will perform ELISA to analyze the cytokines/chemokine changes due to DFMO or chemo-immunotherapy combination during the course of treatment. This testing will be performed using a multiplex cytokine array on a Luminex platform.

39-plex: IL-1 α , IL-1 β , IL-1ra, IL-2, IL-3, IL-4, IL-5, IL-6, IL-7, IL-8, IL-9, IL-10, IL-12 (p40), IL-12 (p70), IL-13, IL-15, IL-17, EGF, Eotaxin, FGF-2, Flt-3-ligand, Fractalkine, G-CSF, GM-CSF, GRO, IFN- α 2, INF- γ , IP-10, MCP-1, MCP-3/CCL7, MDC/CCL22, MIP-1 α , MIP-1 β , TNF α , TNF β , VEGF, sCD40L, TGFas, IL-2R

Single-plex: sIL6-R

14.1.3 Patient Reported Outcomes of Pain

Patients or their proxy for those under the age of 5 years, must complete the Faces Pain Scale-Revised. The Faces Pain Scale-Revised is a simple visual scale validated to provide a real-time (current) pain assessment in the pediatric population.⁵⁷ The scale scores pain based on a visual cue on a scale of 0 to 10.

14.1.3.1 Timing

Administer the Faces Pain Scale Revised at any time on Day -6 (Cycle 1 of Regimen B only) and Day 1 of therapy with irinotecan and temozolomide alone, and then on Days 2-5 of therapy at least 4 hours after the dinutuximab infusion has begun. It will be administered during Cycles 1, 2, 4, 6 for all patients and Cycle 12 of therapy for patients enrolled prior to Amendment 4.

14.1.3.2 Assessments

The assessments will be performed by the nurse caring for the patient at the appropriate time-points described above. The data will be entered in RAVE. The total daily intravenous narcotic dose will also be entered in RAVE.

14.2 **Optional Studies**

The following correlative studies are optional, but **strongly encouraged**. All patients will be eligible for all special studies on ANBL1821.

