Preliminary studies evaluating rat models of allodynia demonstrate that DFMO may reduce dinutuximab induced pain sensation (personal communication, [name]). Furthermore, pro-inflammatory cytokines have been linked to neuropathic pain and the immunomodulatory effects of DFMO may influence such cytokine levels.⁵⁶ Therefore, the association between inflammatory serum cytokine levels (IL1, IL6, TNF-alpha, IFN-gamma, etc.), pain, and DFMO therapy merit evaluation. This exploratory aim is to examine the change in pain during dinutuximab infusion in the patients on the DFMO arm compared to the control arm as determined by the Faces Pain Scale. Patients over the age of 5, and proxy for those under the age of 5, will complete the Faces Pain Scale-Revised on Day 1 of chemotherapy with irinotecan and temozolomide, and then daily during the dinutuximab infusion. This will be measured during Cycles 1, 2, 4, and 6. Patients enrolled prior to Amendment 4 will also have the Faces Pain Scale-Revised collected during Cycle 12 of therapy. The Faces Pain Scale-Revised is a simple visual scale validated to provide real-time pain assessment in the pediatric and adolescent and young adult (AYA) population.⁵⁷ It has been recommended as the superior PRO measure for pain in pediatric populations based on its excellent psychometric properties and responsiveness to change.⁵⁸ The scale scores pain based on a visual cue on a scale of 0 to 10. Pain will also be assessed by measuring the amount of intravenous narcotic administered during the dinutuximab infusion. Patients will also be evaluated for differences in pro-inflammatory cytokine levels during dinutuximab infusion.

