- Use of a patient controlled analgesia device (PCA) or continuous opioid infusion during the dinutuximab infusion is recommended. Morphine is the most commonly administered opioid. May use hydromorphone or fentanyl in patients with known indications for use of hydromorphone or fentanyl. If the patient tolerates the dinutuximab infusion without difficulty, may consider removing the continuous opioid infusion rate in between dinutuximab doses (when dinutuximab is not infusing).
- Recommended starting dose of analgesics:

- Morphine 0.1 mg/kg/dose 20 minutes prior to initiation of dinutuximab infusion. At the same time, start a continuous morphine infusion of 0.02 mg/kg/hr with bolus doses of 0.01 mg/kg/dose q15 minutes prn for pain.
- If hydromorphone PCA is used, recommend hydromorphone pre-infusion dose of 0.02 mg/kg/dose 20 minutes prior to starting the infusion of dinutuximab. At the same time, start a continuous hydromorphone infusion of 0.004 mg/kg/hr (maximum initial rate: 0.2 mg/hour for opioid naïve patients) with bolus doses of 0.002 mg/kg/dose q15 minutes prn for pain.
- If fentanyl PCA is used, recommend fentanyl 1 mcg/kg 10 minutes prior to starting dinutuximab infusion. At the same time, start a continuous fentanyl infusion of 0.5 mcg/kg/hr with bolus doses of 0.25 mcg/kg/dose q10 minutes prn pain.
- Doses should be titrated as needed in accordance with institutional guidelines.

For patients unable to use a PCA, a continuous basal infusion of morphine (or alternative medication) and as-needed boluses of the same medication may be used. Starting doses of the basal infusion and boluses should be based on patient weight, institutional standard practices, and doses required by individual patients for treatment of pain associated with previous interventions.

Have immediately available during the dinutuximab infusion:

- a. Albuterol and oxygen
- b. Epinephrine
- c. Hydrocortisone: Use only for life-threatening reactions (hypotension, bronchospasm, angioedema involving the airway) not responsive to other measures.

Monitoring during the dinutuximab infusion:

- Check vital signs every 15 minutes for the first hour; if stable check vitals hourly until dinutuximab infusion is complete
- Strict intake and output every 4 hours
- Call front line clinician for:
 - a. Altered blood pressure (refer to baseline values for patient and normal values for age/sex/height of patient), tachycardia, tachypnea, fever

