To assess exploratory aim [1.3.3](#), the occurrence of pain on each regimen as reported by patient report and opiate use will be descriptively summarized. Descriptive and summary statistics will be used to describe the scores from the Faces Pain Scale-Revised during the dinutuximab infusion and on Day 1 with irinotecan and temozolomide alone for each arm separately. Confidence intervals will be constructed for the mean and frequency estimates. The Day 1 patient reported outcome data are expected to be similar between the 2 regimens, while differences during or after completion of treatment may be observed.

9.4 **Evaluability for Response**

All eligible patients will be considered evaluable for response.

9.5 **Evaluability for Toxicity**

All eligible patients will be evaluable for toxicity from the time of their first treatment with eflornithine, irinotecan, temozolomide, or dinutuximab.

The study committee will review ototoxicity data closely during monthly committee meetings. If a difference in the incidence of hearing loss of $>15\%$ in eligible patients treated on the interrupted schedule enacted with Amendment 2A is detected among patients on the DFMO-containing Regimen B as compared to Regimen A, the study committee will notify the DSMC and CTEP and discuss potentially suspending accrual and further modifying the DFMO dose and/or schedule. In this context, hearing loss is defined as “an increase of 15dB or more from baseline in hearing threshold at two contiguous frequencies between 500-3000Hz” as this is the criterion for which DFMO is held for hearing loss.

9.6 **Gender and Minority Accrual Estimates**

The gender and minority distribution of the study population is expected to be:

DOMESTIC PLANNED ENROLLMENT REPORT								
Racial Categories	Ethnic Categories						Total	
	Not Hispanic or Latino		Hispanic or Latino					
	Female	Male	Female	Male				

American Indian/ Alaska Native	0	0	0	0	0
Asian	0	3	0	0	3
Native Hawaiian or Other Pacific Islander	0	0	0	0	0
Black or African American	8	5	0	0	13
White	18	29	5	10	62
More Than One Race	0	0	0	0	0
Total	26	37	5	10	78

INTERNATIONAL (including Canadian participants) PLANNED ENROLLMENT REPORT						
Racial Categories	Ethnic Categories				Total	
	Not Hispanic or Latino		Hispanic or Latino			
	Female	Male	Female	Male		
American Indian/ Alaska Native	0	0	0	0	0	
Asian	0	2	0	0	2	
Native Hawaiian or Other Pacific Islander	1	1	0	0	2	
Black or African American	0	0	0	0	0	
White	4	7	2	0	13	

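### Exploratory aim 1.3.3: pain scores and IV narcotic are described as measured during the dinutuximab infusion, but the collection rules confine neither to it

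*Combined protocol and SAP*

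**What the plan says.** **What is to be measured.** Section 2.6.3 has the Faces Pain Scale-Revised completed on Day 1 "and then daily during the dinutuximab infusion". For opioids it says: "Pain will also be assessed by measuring the amount of intravenous narcotic administered during the dinutuximab infusion". Section 9.3.4 plans to summarise "scores from the Faces Pain Scale-Revised during the dinutuximab infusion and on Day 1", for each arm separately and descriptively, with confidence intervals for means and frequencies.

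**What is to be collected.** Section 14.1.3.1 times the score on Day 1 and "then on Days 2-5 of therapy at least 4 hours after the dinutuximab infusion has begun". The observation lists in Sections 4.4.2, 4.5.2, 4.6.2 and 4.7.2 repeat this lower limit, and none gives an end. Section 14.1.3.2 covers the opioid in one sentence: "The total daily intravenous narcotic dose will also be entered in RAVE". Section 14.1.3 describes the scale as "validated to provide a real-time (current) pain assessment in the pediatric population".

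**Context.** The infusion takes 10 hours and may be extended to 20 (Section 4.4.3). Where the patient has tolerated the infusion without difficulty, Section 4.4.4 says sites "may consider removing the continuous opioid infusion rate in between dinutuximab doses (when dinutuximab is not infusing"; this is optional. Section 5.2.5.7 foresees some patients needing IV narcotics for 48 hours or more after dinutuximab is complete.

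**The concern.** The purpose stated in Section 2.6.3 is to compare infusion pain between the DFMO and control arms. Two things prevent the data rules from delivering that.

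- **Score.** The scale records pain at the moment it is used, so a score taken in the evening after a 10-hour infusion has ended says nothing about pain during it. Such a score still meets Section 14.1.3.1 and would enter the Section 9.3.4 summary as a during-infusion value.
- **Opioid.** A daily total cannot be split afterwards into on- and off-infusion parts. Section 14.1.3 does not tie either value to infusion start and stop times, and it does not say whether the day is a calendar day or 24 hours from the start of the infusion.

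If DFMO affects infusion pain only, mixing in off-infusion time shrinks the visible difference and adds noise. Bias would need something more: a difference between arms in infusion length or in how opioids are weaned. Infusion length is a post-randomisation quantity, since it is extended for toxicities such as hypotension or tachypnea.

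**Working it through.** **Infusion length.** Section 4.4.3 gives 17.5 mg/m², run at 0.88 mg/m²/h for 0.5 h and then up to 1.75 mg/m²/h. Without the slow start, 17.5 / 1.75 = 10.0 h. With it, 0.5 + (17.5 − 0.44) / 1.75 = 10.25 h. This reproduces the stated 10 hours. The stated maximum is 20 hours.

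**Share of the permitted score window that falls after the infusion.** The window opens at hour 4. Its close is not stated, so two assumptions are shown.

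*Window runs to hour 24.* Length 20 h; post-infusion share = (24 − T) / 20.
- T = 10: 14/20 = 70%
- T = 20: 4/20 = 20%

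*Window ends at midnight, T = 10, assumed start times (Section 4.4.3 recommends a morning start).*

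| Start | Window | Infusion ends | Post-infusion share |
|---|---|---|---|
| 08:00 | 12:00–24:00 (12 h) | 18:00 | 6/12 = 50% |
| 09:30 | 13:30–24:00 (10.5 h) | 19:30 | 4.5/10.5 = 43% |
| 12:00 | 16:00–24:00 (8 h) | 22:00 | 2/8 = 25% |

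For T = 20 with the same starts and a midnight close, the share is 0%.

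These are shares of permitted time. They do not forecast when nurses will take the score.

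**Share of a daily opioid total that is off-infusion.** Inputs from Section 4.4.4: morphine pre-dose 0.1 mg/kg, then 0.02 mg/kg/h. Assumptions: no boluses, no titration, a 24-hour day, pre-dose counted as on-infusion.
- On-infusion amount: 0.1 + 0.02 × 10 = 0.30 mg/kg at 10 h; 0.1 + 0.02 × 20 = 0.50 mg/kg at 20 h
- Daily total, background continued: 0.1 + 0.02 × 24 = 0.58 mg/kg
- Off-infusion share: (0.58 − 0.30) / 0.58 = 48% at 10 h; (0.58 − 0.50) / 0.58 = 14% at 20 h
- Background stopped when the infusion ends: essentially none

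**Dilution.** Suppose opioid use falls by 30% during the infusion only, against a constant background over 24 hours. In the daily total the fall appears as 0.30 × 10/24 = 12.5% at 10 h and 0.30 × 20/24 = 25% at 20 h. The 30% is illustrative; the documents state no target effect for this aim.

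**Does an on-infusion amount solve the opioid problem?** Not as a raw amount. It moves from 0.30 to 0.50 mg/kg (1.67 times) between a 10- and a 20-hour infusion at the same hourly rate, while the daily total with background continued is 0.58 in both. Per infusion hour it is 0.30/10 = 0.030 and 0.50/20 = 0.025 mg/kg/h with the pre-dose included, and 0.02 in both with it left out.

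**The case against.** The strongest reply is that the sections can be read together. Sections 2.6.3 and 9.3.4 already say during the infusion and Section 14.1.3.1 adds a four-hour minimum, so the score belongs between hour 4 and the end. That is probably the intent. But the sections a nurse works from, Section 14.1.3.1 and the observation lists, carry only the lower limit.

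For opioids, the infusion window appears in the rationale alone. Aim 1.3.3 and Section 9.3.4 speak of opiate usage or use with no window, and Section 9.3.4 allows for differences during or after treatment. A daily total fits those two places. This stands, and it is why relabelling the measure is an acceptable fix.

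Stopping the background opioid is also tied to tolerating the infusion. The daily total therefore carries some information about pain and is not just a record of site habit. This stands too.

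A reader might infer that the data will be mostly off-infusion. The documents do not support that. The opioid share reaches 48% at most on the counting above and passes half only if the pre-dose is counted as off-infusion (0.38/0.58 = 66%). The score window exceeds half only if it runs past midnight to hour 24. A reader might also infer a built-in bias between arms, but both arms follow the same recording rules and essentially the same supportive-care text.

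Finally, the case report forms are not part of the document (Section 12.0 says they are posted elsewhere) and may already hold times. Section 4.4.3 does ask for the duration of an extended infusion to be recorded.

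**Conclusion.** The mismatch is real and small in scope. A score taken after the infusion complies with Section 14.1.3.1 and would be tabulated as infusion pain, and the opioid measure in Section 2.6.3 cannot be recovered from the value that Section 14.1.3.2 collects.

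The exposure is largest at the standard 10 hours and much smaller at 20. All the percentages rest on the stated assumptions about the undefined day, start times and opioid use; they show what the rules permit, and say nothing of what has occurred. The likely consequence is dilution and noise. Bias depends on an arm difference in infusion length or opioid weaning, which the documents neither show nor exclude. The aim is exploratory and descriptive, and the primary endpoint is unaffected. This is an inexpensive improvement rather than a threat to the trial's conclusions.

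**What to change.** **Score.** In Section 14.1.3.1 and the four observation lists, state that the Day 2–5 score is taken no earlier than four hours after the infusion starts and before it ends. Record the time of the score with infusion start and stop times. If an infusion stops before four hours, record that as the reason for having no in-infusion score, because such losses may be informative.

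**Opioid.** Reconcile Sections 2.6.3, 9.3.4 and 14.1.3.2 in one of two ways:
- call the measure total daily IV narcotic throughout, and define the day; or
- also record the on-infusion amount, report it per kg per infusion hour, state whether the pre-dose is included, and keep the daily total as a separate measure.

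**Data already collected.** Limit the during-infusion summary to scores whose recorded time falls within the infusion, where such times exist, and report the rest separately.

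**Cost.** Wording changes and a few form fields, with no extra assessments. Some existing untimed scores would leave the during-infusion summary. The change concerns measurement only; none is proposed to analgesic or infusion management.
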